544 collection of consultation and chlamydia testing data, with patients de-identified but including a
545 unique identification code. As a backup, consent will also be obtained to collect quarterly chlamydia
546 testing numbers from each clinic's pathology provider, and from Medicare Australia, the Australian
547 Government Insurance Scheme that funds chlamydia general practice consultations and chlamydia
548 tests in Australia. The data obtained via the pathology provider or Medicare will not include a unique
549 identification code. The data collected will include chlamydia testing rates for the 12 months prior to
550 trial commencement; chlamydia positivity rates for the 12 months prior to trial commencement,
551 and; number of PID and epididymitis diagnoses for the 12 month prior to trial commencement.
552 During the trial, the data collected will include the number of consultations with 16–29 year olds;
553 the number of chlamydia tests for 16–29 year olds; the number of repeat tests for 16 to 29 year
554 olds; the number of 16–29 year olds testing positive for chlamydia and re-testing following testing
555 positive; the number of PID cases diagnosed among women aged 16–34 years at participating GP
556 clinics and local hospitals; and the number of epididymitis cases diagnosed among men aged 16–29
557 years at participating GP clinics and local hospitals. The number of cases of PID and epididymitis
558 associated with chlamydia will be reported where a laboratory test has been done and the number
559 of PID cases referred to a hospital will also be extracted. The automated data extraction tool
560 provides data from clinics in intervention and control areas in a way that cannot be subverted. This
561 will help to minimise bias in the measurement of chlamydia test uptake and re-testing rates.

562 ***Adverse-events reporting***

563 Patients receiving the intervention could experience adverse events after receiving a diagnosis of
564 chlamydia or from antibiotic treatment. Levels of anxiety and of partnership breakdown in women
565 screened for chlamydia in the USA have been reported to be more common in those receiving a

566 positive than a negative test result [88]. Azithromycin can cause minor gastrointestinal upset, but
567 rarely causes serious side effects [84, 89].

568 During the intervention period passive surveillance for adverse events will be undertaken. The

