569 overall numbers of events in intervention and control clinics will be reported. Diagnoses of anxiety
570 and referrals for psychological or psychiatric treatment will be extracted from the clinics' electronic
571 medical records where possible. However, it will not be possible to assess causality from these data.
572 In the final prevalence survey, the questionnaire administered to patients attending both
573 intervention and control clinics will ask them to report whether they experienced any anxiety or
574 issues with their partner following any chlamydia test they had during the intervention period and
575 whether their chlamydia test result was positive or negative. These data will also be reported.

576 ***Statistical analysis plan***

577 ***Sample size and power calculations***

578 Table 1 summarises the total numbers of randomised clusters required to detect differences in
579 estimated chlamydia prevalence (the primary outcome measure) between intervention and control
580 arms at the end of the trial. The calculations were based on the following assumptions:

- 581 1. The intra-class correlation coefficient (ICC) was estimated from individual practice data to be
582 0.009 [90]. Since combining practices into clusters in the trial design is likely to reduce the ICC,
583 calculations were also performed using ICC = 0.007 and ICC = 0.005.
- 584 2. The design effect (the inflation of the sample size to allow for between area variability) was
585 calculated as $1 + (n - 1) * ICC$, where n is the number of people tested at each area.
- 586 3. All calculations are for 80% power and use a two-sided significance level of 5% [61].

587 Table 1 shows that 54 clusters (27 in each group) are required to detect a difference in chlamydia
588 prevalence between the intervention and control groups of 2% at the end of the trial with 80%
589 power (4% in control and 2% in intervention group). Within each of the geographical areas, 80 men
590 and women aged 16 to 29 years will be tested for chlamydia during each prevalence survey.
591 Statistical power will be increased if a higher than expected chlamydia prevalence is obtained at
592 baseline or if the ICC is lower than estimated. If the ICC is found to be 0.005, 54 clusters will give 89%
593 to detect a difference of 2% at the end of the trial.

594 ***Baseline data***

595 Cluster, clinic and participant baseline characteristics will be summarised by randomised group as

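### Antibiotic treatment is one of two harms the protocol names, yet no defined collection item asks about it; reactions are left to unspecified passive surveillance

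*Protocol*

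**What the plan says.** The protocol deals with harms in one section, Adverse-events reporting. It opens with two sources: "Patients receiving the intervention could experience adverse events after receiving a diagnosis of" "chlamydia or from antibiotic treatment". For the first it cites evidence on anxiety and partnership breakdown. It ends that evidence and turns to the second in the words "positive than a negative test result [88]. Azithromycin can cause minor gastrointestinal upset, but" "rarely causes serious side effects [84, 89".

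Three means of collection follow:

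- A general one: "During the intervention period passive surveillance for adverse events will be undertaken". Totals by arm are to be reported, but the section does not say which events count, who reports them or from what source.
- Extraction from clinic records, where possible, of anxiety diagnoses and of psychological or psychiatric referrals. The protocol adds that causality cannot be assessed from these data.
- The final prevalence survey, in which patients at "intervention and control clinics will ask them to report whether they experienced any anxiety or" partner problems after any chlamydia test during the intervention period, and to say whether the result was positive or negative.

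**The concern.** Both means with named content serve the psychosocial harm. The drug harm, which the section itself raises, has only the general one. A minor reaction that settles before the patient's next visit would often never reach a clinic record, so unprompted surveillance is weakest for exactly the kind of event that the protocol describes.

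Treatment is part of what is being evaluated. The Description of the intervention defines a chlamydia screening intervention as testing, treating those who test positive, and partner notification. The Rationale for the trial says that the benefits of screening must be shown to outweigh its harms. If totals by arm are printed under the label of adverse events, a reader may take few recorded antibiotic reactions to mean that few occurred. Clinics and GPs know their allocation (Blinding), so spontaneous recording could also differ between arms. The gap lies in collection, and no later analysis can recover answers that were never sought.

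**Working it through.** The protocol gives no figure on this point to reproduce. The check is a reading of every collection list, followed by simple arithmetic on what a survey item would yield.

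**Step 1: named harms against defined items.**

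- Harm after a diagnosis: covered by record extraction (anxiety, referrals) and by the survey questions (anxiety, partner problems).
- Harm from antibiotics: no item in either.
- Patient characteristics (survey content): demographics, sexual behaviour, symptoms and testing history; no treatment reaction.
- Chlamydia testing, diagnosis and sequelae data (routine extraction): consultations, tests, repeat tests, positives, PID and epididymitis; no drug reaction.
- Passive surveillance: not restricted by type, so antibiotic events are not excluded, but they are not specified either.

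The count is two named sources of harm, two defined routes that are both psychosocial, no item for antibiotic reactions, and one general statement.

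**Step 2: how many respondents could answer a survey item.**

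Inputs: 27 clusters per arm and 80 people surveyed per cluster (Sample size and power calculations); 30% tested per year and prevalence of about 4% (Aims and Objectives); up to four annual rounds (Intervention); usual testing of 8% per year (Rationale for the trial).

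- Surveyed per arm: 27 × 80 = 2,160.
- Intervention arm, with a positive test: 0.30 × 0.04 × 4 = 0.048; 2,160 × 0.048 = 104.
- The same at 2% positive, the level hypothesised for the end of the trial: 2,160 × 0.30 × 0.02 × 4 = 52.
- Control arm: 0.08 × 0.04 × 4 = 0.0128; 2,160 × 0.0128 = 28.

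These figures assume that respondents were exposed to all four rounds, that they were tested at the target rate, that positivity among those tested equals the prevalence figure, and that nobody is counted twice. They give the order of magnitude only.

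**Step 3: what those numbers can support.**

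If none of n respondents reported a reaction, the one-sided 95% upper limit for the reaction rate, ignoring clustering, is 1 − 0.05^(1/n).

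- n = 104: 1 − 0.05^(1/104) = 2.8%.
- n = 28: 1 − 0.05^(1/28) = 10.1%.

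The item can therefore roughly bound how common reactions are in the intervention arm. It cannot support a comparison between arms.

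**The case against.** The best defence is that this is a proportionate choice. The randomised intervention is organised testing, not a drug. Azithromycin is presented as the existing first-line treatment (Chlamydia diagnosis and case management), and control clinics continue usual care (Control group). Its effects are described as minor and rarely serious. Specific questions were kept for the less familiar psychosocial harms, with drug events left to general surveillance. A reaction that brings the patient back, or a serious one, is something passive surveillance can catch. All of this stands, and it is why the point is not an error or a contradiction. It does not explain why that surveillance has no stated events or source, or why a harm that the protocol names goes unasked in a survey that already asks about harm after a test.

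Two stronger readings are tempting, and the documents do not support either:

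- A reader might infer that the trial will report nothing on treatment harm, or has no means of detecting it. The general surveillance statement follows directly after the azithromycin sentence, is not limited to psychosocial events, and comes with reported totals by arm. Incomplete is supported; silent is not.
- A reader might try to count the missed reactions, for example from 27 × 500 × 0.30 × 0.04 = 162 treated per year. The 500 is a cluster-eligibility minimum of residents aged 15 to 29, whereas testing uptake is measured among attenders aged 16 to 29, so 162 is not a floor. It is also gross: usual testing alone would give 27 × 500 × 0.08 × 0.04 = 43, leaving about 119 extra. The protocol gives no reaction rate, so any event count would rest on an assumption from outside it.

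The objection that a survey item would yield few positives also stands, and it limits the item to descriptive use.

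**Conclusion.** The point holds as a gap in collection. Antibiotic treatment is one of the two sources of harm that the protocol names, and every item with defined content covers the other one. Capture of antibiotic reactions rests on passive surveillance whose events and source are not stated, so the totals are likely to be incomplete for treatment harm, particularly for minor reactions.

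The size of the shortfall cannot be derived from the protocol. That totals will be incomplete is a judgement about unprompted reporting, not a calculated result. What can be sized is the remedy: about 100 intervention-arm respondents with a positive test, about half that at 2% positivity, and under 30 in the control arm, all on the assumptions in the working. The point is worth acting on as a cheap improvement. It does not touch the primary comparison.

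**What to change.** 1. In the final questionnaire, add one item for respondents who report a positive test: did they have any reaction to the treatment they took? The survey already asks whether the result was positive, so the filter exists. Report the answers descriptively by arm, per 100 respondents with a positive test, without a hypothesis test.
2. Where the extraction tool is installed, also extract recorded adverse drug reactions dated after a positive chlamydia test, in both arms.
3. If neither is done, state in the results that antibiotic reactions were not systematically collected, so that the event totals are not read as covering them.

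The cost is one question and one further extraction item. The downsides are recall error over a period of up to four years, few positive respondents, and drug-reaction fields that may be incompletely filled. Clinics that rely on backup pathology or Medicare data have no unique patient code, so reactions there cannot be linked to an earlier positive test. These are acceptable for descriptive reporting and should be stated beside the results. Nothing in the change alters treatment.

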175 chlamydia testing rates [61]; testing increased by 60% in intervention clinics vs. 7% in control clinics
176 ($p < 0.01$). In Australia, a simpler intervention involved only a computer alert prompting GPs to
177 discuss chlamydia screening with 16 to 24 year olds; the proportion of women tested increased
178 more in intervention (from 8 to 12% after 12 months) than control clinics (from 9 to 11%, odds ratio
179 1.3, 95% CI: 1.1, 1.4) [62].

180 There has been one RCT investigating the impact of incentive payments (\$5 to \$8 (AUD) per test) to
181 GPs for each chlamydia test ordered, but this failed to find an effect [63]. However, this trial was
182 inadequately powered and payments were not made until the end of the 12 month trial when GPs
183 had little recollection of their participation. Systematic reviews evaluating the impact of financial
184 incentives targeting preventive care and/or chronic disease management activities, each with
185 different inclusion/exclusion criteria [64-69], unanimously conclude that the effects on quality of

186 care and patient outcomes remain largely uncertain because of serious methodological weaknesses.
187 Some individual studies have found small incremental benefits. RCT evidence has demonstrated
188 modest improvements in vaccination rates over usual care with absolute increases of 7.8% in a US
189 study of immunisation in the elderly (additional payment of \$0.80 (USD) to \$1.20 (USD) per shot to
190 provider) [70] and 9.9% in a US study of immunisation in children (\$5 per shot plus \$15 per patient
191 visit to provider) [71], although this latter study included enhanced provider feedback as part of the
192 intervention. A controlled before and after study in the US among clinics receiving a payment of
193 US\$0.23 per patient per month for each performance target that was met or exceeded, found that
194 there was a small but significant improvement for cervical screening (3.6% higher screening rate in
195 intervention compared with control, $p=0.02$), but for mammography or glycosylated haemoglobin
196 monitoring, there was no difference between the intervention and control groups [72].

197 ***Rationale for the trial***

198 Before introducing a screening programme, evidence from high quality randomised controlled trials
199 (RCTs) is needed to show that the benefits of screening, with sufficient participation rates, outweigh

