405 The trial statistician generates the randomisation sequence using a computer-generated
406 minimisation algorithm according to the following baseline variables:

- 407 • Location (State);
- 408 • Estimated baseline chlamydia prevalence;
- 409 • Estimated overall baseline testing rate;
- 410 • Estimated percentage of population aged 16 to 29 years.

411 ***Allocation concealment***

412 Concealment of the computer-generated randomisation sequence until allocation will minimise
413 selection bias. The trial statistician will be located at a site away from any of the participating
414 geographical clusters. The statistician allocates each cluster according to the computer-generated
415 minimisation algorithm when data on all baseline variables are available. The statistician informs

416 research staff of the cluster allocation, and research staff, in turn notify, all general practice clinics
417 and AMSs in the cluster of the allocation.

418 ***Blinding***

419 Blinding of clinics and GPs to their trial allocation is not possible given the nature of the intervention.
420 Patients attending participating clinics will be made aware that the clinic is taking part in a trial of
421 chlamydia testing via posters and information cards available in the waiting room but will not be told
422 whether they are in an intervention or control cluster.

423 Pathology providers that conduct chlamydia tests will not be deliberately blinded but will not be told
424 explicitly whether participating clinics are in intervention or control clusters.

425 Assessment of PID and epididymitis as clinical outcomes will be performed by an endpoint
426 assessment committee that is blinded to whether the woman is in an intervention or control cluster.
427 This will help reduce bias in the clinical diagnosis of PID.

428 The trial statistician will conduct a blinded analysis of the primary outcome.

429 ***Trial endpoints***

430 ***Primary endpoint***

431 **Chlamydia prevalence in clinic attenders**

432 The primary biological endpoint is estimated chlamydia prevalence in the population served by the
433 clinics. Chlamydia prevalence will be estimated at baseline (pre-trial) and at the end of the
434 intervention period. Prevalence is estimated as the proportion (with 95% CI) of 16 to 29 year old
435 women and men attending a participating clinic who have ever had sex who test positive for
436 chlamydia.

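### Harms are to be reported as event counts by arm without a denominator, and the caveat on causality is broader than a cluster-randomised design warrants

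*Protocol*

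**What the plan says.** The Protocol, under adverse-events reporting, names distress and relationship breakdown after a diagnosis, and antibiotic side effects, as possible harms. It then sets out three elements.

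- Passive reporting: "During the intervention period passive surveillance for adverse events will be undertaken", and the "overall numbers of events in intervention and control clinics will be reported".
- Record extraction: anxiety diagnoses "and referrals for psychological or psychiatric treatment will be extracted from the clinics' electronic" medical records, where this can be done. The next sentence says that "it will not be possible to assess causality from these data".
- Final survey: patients in both arms are asked about anxiety or partner problems following any chlamydia test during the intervention period, and whether that test was positive. These answers are also to be reported.

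The only size-related variable in the minimisation is "Estimated percentage of population aged 16 to 29 years". The others are state, baseline prevalence and baseline testing rate.

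PID and epididymitis are treated differently. Their endpoint definitions divide cases by patients with at least one consultation, and the section on statistical tests plans incidence per 100 patients seen with Poisson regression. Harms do not appear in that list of outcome analyses.

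**The concern.** The rationale for the trial says that randomised evidence is needed to weigh the benefits of screening against its harms. The benefit will be expressed as a contrast between randomised arms. For harms, the stated summary is a number of events in each arm, which depends on how many patients each arm saw and how many clinics yielded records, as well as on risk. A difference in counts could then be read as harm when there is none, or a real difference could be set aside because the section has already said that causality cannot be assessed.

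The caveat is also not limited to what it can support. Nobody can say whether one recorded anxiety diagnosis was caused by a chlamydia test. A difference in rates between randomised groups of clusters is another matter: it estimates the effect of allocation, with whatever bias unblinded recording brings. The Protocol accepts this reasoning for PID. It concedes that ascertainment bias by GPs cannot be removed, yet still plans a modelled comparison of incidence.

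**Working it through.** The Protocol gives no figure for harms, so there is none to reproduce. The check asks how far raw counts can differ between arms when risk is equal.

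**Inputs from the Protocol.** There are 27 clusters per arm (sample size section). Each cluster has at least 500 residents aged 15 to 29 and at most six general practice clinics (cluster criteria), so sizes can vary. Patient numbers are not a minimisation variable.

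**Assumptions, not in the Protocol.** Coefficient of variation (CV) of patients per cluster 0.3 to 0.8; mean of 1,000 patients per cluster; event risk 2 to 10%.

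**Step 1: fixed example.** At a 5% risk in both arms, 29,700 patients against 27,000 give 29,700 × 0.05 = 1,485 events against 27,000 × 0.05 = 1,350. The count ratio is 1.10 and the rate ratio 1.00.

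**Step 2: chance imbalance in arm size.** The SD of the log ratio of arm totals is approximately CV × √(1/27 + 1/27) = CV × √(2/27) = CV × 0.272.

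- CV 0.4: 0.109
- CV 0.6: 0.163
- CV 0.8: 0.218

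So one SD is about 11 to 22%, with 16% in the middle.

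**Step 3: simulation.** 20,000 allocations of 27 against 27 clusters, lognormal sizes, Poisson events, and the same 5% risk in both arms. The ranges are the central 95%.

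| Size CV | Raw count ratio | Rate ratio | Arm sizes more than 10% apart |
|---|---|---|---|
| 0.3 | 0.84–1.19 | 0.93–1.08 | 24% |
| 0.5 | 0.76–1.31 | 0.93–1.08 | 49% |
| 0.8 | 0.65–1.54 | 0.93–1.08 | 65% |

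At 2% risk the rate ratio range is 0.89–1.13; at 10% it is about 0.95–1.06. The simulation uses simple random allocation, so any indirect balance in size from the minimisation is ignored. It also leaves out variation in event risk between clusters, which would widen both ranges.

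**Step 4: what a rate could detect.** The Protocol's hypothesis is 30% tested, current testing is put at 8%, and prevalence is 2 to 4%. Extra positives are (0.30 − 0.08) × 0.02 to 0.04 = 0.0044 to 0.0088 of attenders per year. Assume that 10% of them gain a recorded event, against a 5% background. The rate ratio is then 1 + 0.00044/0.05 to 1 + 0.00088/0.05, or 1.01 to 1.02. With a background of 2 to 10% it is 1.004 to 1.044. These values lie inside the null range of step 3 at 5% risk, so a denominator makes the comparison fair but not sensitive to a small effect.

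**The case against.** The strongest reply is that this is a descriptive safety summary whose denominator, model and interval would normally sit in an SAP, which is not at hand. The absence of a model is indeed no finding. But the Protocol states a summary measure and a limit on inference, and both can be judged as written. It is also fair that the sentence on overall numbers follows the one on passive surveillance, and that no format is fixed for the extracted diagnoses. It remains the only format the section gives for either.

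A second reply is that the final survey already supplies harms data in both arms, from about 80 patients per cluster. A reader might infer that harm will be available only as two bare counts; the survey shows that this is not so. It does not close the gap, though. The question covers only harm following a test, and an analysis among tested patients would condition on testing, which is what the intervention changes.

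A third reply is that the causality sentence is right for records kept by unblinded GPs and extracted incompletely. That stands for individual events, and as a warning about differential recording, which a denominator does not cure.

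Three further inferences are not supported. The randomised comparison is not thrown away, because events are shown by arm. Nothing says that intervention clinics will report more events passively; the quarterly feedback concerns testing rates. And nothing says that anxiety diagnoses or referrals are linked to the patient code and test results: the code is described for "collection of consultation and chlamydia testing data, with patients de-identified but including a" unique identifier, and linkage to test results is stated for PID and epididymitis. A comparison before and after testing therefore cannot be assumed feasible, and it would not be a randomised contrast.

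**Conclusion.** The point holds in a limited form. The stated summary of harms is a count by arm, which mixes risk with arm size and extraction coverage, and the caveat on causality extends to an arm-level comparison that the design can inform. Chance differences in arm size of about 11 to 22% at one SD rest on an assumed cluster-size CV of 0.4 to 0.8. The direction of the problem does not depend on that assumption; its size does. Incomplete extraction could add to the difference by an amount that the Protocol does not allow one to estimate.

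A reader might go further and conclude that the trial cannot speak to harm at all. The Protocol does not support that: reporting is by randomised arm, the survey adds a second source, and consultation data that could supply a denominator are already collected. The primary outcome and its analysis are not affected.

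**What to change.** Replace the overall numbers with new anxiety diagnoses and psychological or psychiatric referrals per 100 patients aged 16 to 29 seen, by randomised arm, in clinics and periods where records are extracted. Give a cluster-adjusted 95% confidence interval from the Poisson approach already planned for PID, and state how many clinics in each arm contribute. The testing-uptake endpoint already counts unique patients aged 16 to 29 with a GP consultation, so the denominator needs no new data. Limit the causality sentence to individual events and to possible differences in recording between unblinded arms. Keep the survey results as a separate source, described as harm that patients report after a test.

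The cost is a change of wording and one more model. Clinics without extraction drop out of this comparison, and the interval may be too wide to detect a small effect, which the report should say.
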